		
alcohol use.
 
Subject will be screened for the following STIs during the enrolment visit: HIV, syphilis, hepatitis A/B/C, Chlamydia trachomatis, Neisseria gonorrhoea, and Mycoplasma genitalium.
 
Participants will be asked to return approximately one week later to discuss their HIV result and whether they wish to proceed with initiation of PrEP.
 
The decision regarding initiation of continuous or intermittent PrEP is based on a discussion with the subject and study team (doctor/nurse), subjects' personal preference, medical considerations and whether the expected use will surpass more than 15-20 tablets of FTC/TDF per month.
 
HIV testing will be repeated at 2, 4 and 8 weeks from the most recent high risk exposure (for HIV acquisition) prior to initiation of PrEP. Thereafter participants are requested to visit the clinic every 3 months from PrEP initiation (for the next 24 months) for HIV & STI testing, evaluation of compliance (blood test for drug monitoring in continuous PrEP arm, drug diaries in both continuous and intermittent PrEP arms), assessment of clinical and/or biochemical adverse reactions and quality of life and sexual behaviour assessment. Subjects will be asked to answer the same questions regarding sexual behaviour and quality of life at follow up visits as at inclusion study visit.

Statistics	Sample size	Not applicable
	Methods	Categorical variables will be described by means of absolute and relative frequencies, while continuous variables by means of mean, standard deviation, quartiles, min and max.

LIST OF ABBREVIATIONS

AE	Adverse Event
ART	Anti retroviral therapy
COHP	Country of high prevalence of HIV
CRA	Clinical Research Associate
CRF	Case Report Form
CSR	Clinical Study Report
CT	Chlamydia trachomatis
DM	Data Manager
EC	Ethics Committee
eCRF	Electronic Case Report Form
EDC	Electronic Data Capture
EMA	The European Medicines Agency
GCP	Good Clinical Practice
HIV	Human Immunodeficiency Virus
ICF	Informed Consent Form
ICH	International Conference on Harmonisation
IMP	Investigational Medicinal Product
ISF	Investigator Site File
ITT	Intention-To-Treat
MG	Mycoplasma genitalium
MSM	Men who have sex with men
NG	Neisseria gonorrhoea
PI	Principal Investigator
PIS	Patient Information Sheet
PrEP	Pre-Exposure Prophylaxis
SAE	Serious Adverse Event
SD	Standard Deviation
SDV	Source Data Verification
SUSAR	Suspected Unexpected Serious Adverse Reaction
STI	Sexually Transmitted Infections

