4.3 Adverse Events and Serious Adverse Events

4.3.1 General

The Investigator should ask the subject questions during the clinic visits in order to ensure that appropriate adverse event information is recorded in the subject's source notes and is then subsequently entered into the CRF. Adverse events will be recorded in response to the following question - "Since you were last asked have you felt unwell or different from usual in any way?" All relevant responses from the subject will be recorded in the CRF on an adverse

event form and graded on severity, seriousness and relationship to study medication. For further details regarding the classification of adverse events see below.

Subjects will be questioned regarding any signs and symptoms occurring in the screening period and for baseline signs and symptoms prior to the first dose of study medication on Day 1. Subjects will subsequently be questioned regarding adverse events throughout the study. All adverse events are to be reviewed by the Investigator while on-going and subsequently documented at the point of resolution. All adverse events classified as serious are to be immediately brought to the attention of the Investigator by site staff for review and action in accordance with Section 4.4.5 below.

All on-going adverse events will be followed up by the Investigator until subject discharge or resolution. Additional clinic visits may be scheduled by the Investigator to follow-up on adverse events according to their clinical judgement.

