4.3.6 Reporting of suspected unexpected serious adverse reactions by Investigator

Suspected unexpected serious adverse reactions (SUSARs) will be reported by the investigator according to appropriate Competent Authority and Ethics Committee requirements. SUSAR reporting to the Competent Authorities and Ethics Committees will be performed in writing using CIOMS forms, according to local regulations.

Fatal and life-threatening SUSARs should be reported as soon as possible to the Competent Authorities and Ethics Committees according to local regulations, and in any case no later than seven calendar days, after knowledge by Investigator of such a case. Relevant follow-up information on the case will be subsequently communicated within an additional eight days. All other SUSARs shall be reported to the Competent Authorities concerned and to the Ethics Committee concerned according to local regulations as soon as possible but within a maximum of fifteen days of first knowledge by Investigator.

In addition to the first evaluation of an adverse event that is performed by the investigator, a second evaluation with respect to seriousness, causality and expectedness and a risk-benefit assessment is performed by ISCR to process safety evaluation according to a four-eye principle.

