6 VARIABLES

- Demographic information (age, gender, race, height, weight, sexuality, education, work situation, relationship status)
- Sexual behaviour (number of partners, condom use, HIV positive partners)
- Sexual transmittable infections (history and current status for infections with syphilis, hepatitis A/B/C, *Chlamydia trachomatis*, *Neisseria gonorrhoea*, and *Mycoplasma genitalium*).
- Compliance (days tablets taken, days tablets missed, compliance (%), compliance in connection with exposure to infection, reason for poor compliance, serum concentration of FTC/TDF).
- HIV infection status (positive, negative, resistance)
- Quality of Life using attached questionnaire
- Adverse reaction related to PrEP treatment

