7.2 Study Populations

Data will be described on enrolled subjects undergoing PrEP treatment. Subjects who do not satisfy inclusion criteria will not be included in the analysis. A summary table reporting reasons for exclusion will be provided.

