7.5 Data Collection / Case Report Forms

Data will be collected using an electronic data capture (EDC) solution. Electronic Case report forms (eCRFs) will be utilised for recording data from each subject meeting the eligibility criteria but will not be completed for subjects who fail to meet eligibility criteria. The eCRF system, VieDoc™, will be available on an internet portal accessible through any standard computer with internet access. A personal log-in will be provided for all responsible personnel to allow for an audit trail relating to the study data to be maintained.

For the subject questionnaire at 3 months follow-up and the subject diary there will be an option to complete these electronically through the app ViedocMe™ on a smart phone.

The data in the eCRFs should be consistent with the relevant source documents. The Investigator will sign the designated signature fields of the eCRF data entry screens to confirm that the information on each screen is accurate and complete. All data must be stored in an unidentifiable form treated with strict confidentiality in accordance with applicable data protection regulations.

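### Section 7.2 defines no all-treated safety set, and Sections 7.2, 7.5 and Table 1 disagree on who is excluded and what is recorded about them

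*Protocol*

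**What the plan says.** Section 7.2 of the protocol names one population: "Data will be described on enrolled subjects undergoing PrEP treatment". It continues "Subjects who do not satisfy inclusion criteria will not be included in the analysis", and then "A summary table reporting reasons for exclusion will be provided". SAP Section 7.2 carries the same text. Neither document defines a separate safety population.

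Section 7.5, also the same in both documents, says that eCRFs "will not be completed for subjects who fail to meet eligibility criteria".

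Section 6 lists "Adverse reaction related to PrEP treatment" among the variables. Table 1 schedules adverse-event collection at week 4, at follow-up and extra visits and at the end of study. It schedules the eligibility assessment at Visits 0 and 1, and its first footnote asks for the assessments in the table to be captured in the database when they are done.

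**The concern.** A safety summary should describe everyone exposed to the drug. A set restricted by entry criteria does not, because a person can take FTC/TDF and be found afterwards not to have qualified. Under 7.2 that person's adverse reactions do not appear in any reported table.

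The data-capture rule adds a second difficulty. Section 7.2 filters on inclusion criteria, while 7.5 filters on eligibility criteria, which cover inclusion and exclusion. The two rules can give different answers for the same subject. Section 7.5 also withholds the eCRF from the people whom the exclusion table in 7.2 has to describe. For a study of how PrEP is implemented, the number turned away and the reasons are informative in themselves.

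**Working it through.** No arithmetic applies. The Protocol Outline gives the sample size as "Not applicable", the plan is descriptive, and neither document gives a number of ineligible or treated-then-ineligible subjects. The check is to take each kind of subject through the rules as written.

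**1. Found ineligible at screening, no study-prescribed dose.** Section 7.5: no eCRF. Table 1: the eligibility assessment goes into the database. Section 7.2: if an inclusion criterion is failed, the subject belongs in the table of reasons. The 7.5 rule and Table 1 conflict, and no screening log or screen-failure form is mentioned as another source. The CRF entry in Section 3.5 records reasons for withdrawal, which is a different thing.

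**2. Dosed, then found not to meet an inclusion criterion.** Section 7.2 removes the subject from all summaries, adverse reactions included. An eCRF would normally have been opened while the subject was thought eligible. Section 7.5 does not say whether it continues.

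**3. Dosed, then found to have met an exclusion criterion at entry.** HIV infection undetected at the start is the example the documents foresee. Section 4.1 gives a 12-week window for ruling out infection and does not recommend waiting for it. Section 4.2 schedules tests at weeks 2, 4 and 8 to find people seroconverting at inclusion. Section 3.2 makes HIV positivity an exclusion criterion. Read literally, 7.2 keeps this subject because no inclusion criterion is failed, 7.5 provides no eCRF because eligibility is failed, and Section 3.5 registers a PrEP failure. The three sections do not combine into one instruction.

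**4. Contraindication known at entry.** Section 3.2 excludes those who cannot take FTC/TDF because of contraindications. Section 5.3 allows patients with a contraindication to be included if they are put on FTC/TDF. Whether such a subject counts as eligible is unresolved, so the effect of 7.5 is too. The two sections must be reconciled.

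**5. Already on PrEP at enrolment.** Sections 3.4 and 4.1 admit these subjects and collect their history back to the start of PrEP. Exposure precedes the eligibility check, and 7.2 does not say how that exposure counts in a safety summary.

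**How often this could arise.** Entry under Section 3.1 needs criterion 1 plus any one of criteria 2 to 7, and criterion 3 is the provider's own judgement that PrEP is indicated. Few treated adults would fail that.

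**What is held elsewhere.** Section 4.3.1 requires that "appropriate adverse event information is recorded in the subject's source notes" before entry in the CRF. Section 8.3 requires safety data in the subject's record. Section 4.3.6 states "SUSAR reporting to the Competent Authorities and Ethics Committees will be performed in writing using CIOMS forms". Under Section 4.3.5, however, a SUSAR must be both serious and inconsistent with the product characteristics, so expected or non-serious reactions do not travel by that route. Section 7.1 places all analyses after database lock, and no route is stated from source notes into the analysis for an event that is not in the eCRF.

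**The case against.** The strongest reply is that 7.2 literally removes only subjects who fail inclusion criteria. Those concern age, being offered or having started PrEP, and HIV risk; drug tolerability is not among them. Safety is also not one of the five objectives, the study is uncontrolled for adverse reactions, and Section 7.1 defers detail to a separate document that is not available, which might define a safety set. All of this limits the importance of the point. It does not remove it, because the available text in both documents states the restriction outright and lists adverse reactions for reporting.

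Three stronger readings are tempting and are not supported.

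- A reader might infer that adverse-event data are lost. They are omitted from a summary. The events remain in source notes and medical records, and SUSARs are reported on their own forms.
- A reader might infer that the exclusion table cannot be built. Table 1 puts the eligibility assessment in the database, and a subject found ineligible after starting would normally already have an eCRF. What can be said is that the table has no stated source and that 7.5 contradicts Table 1.
- A reader might infer that the people removed are those most likely to react to the drug, so that reported frequencies are too low. Contraindications are exclusion criteria, which 7.2 does not literally cover, and nothing suggests more reactions among people who fail a risk criterion. A contraindication that emerges after the start is not a failure of entry criteria assessed at Visits 0 and 1, so such a subject keeps an eCRF.

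**Conclusion.** The point holds as a defect in the definition of the analysis set and in consistency between sections. The single restricted set omits adverse reactions in treated subjects who fail inclusion criteria. Sections 7.2 and 7.5 apply different terms. Section 7.5 conflicts with Table 1, is silent on the eCRF of treated subjects later found ineligible, and leaves the exclusion table without a named source.

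The number affected is probably small, given the breadth of criterion 3. No size or direction of bias should be claimed. The conclusion assumes that the separate document mentioned in Section 7.1 does not already define an all-treated set. It should be corrected, but it does not threaten the study's main objectives.

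**What to change.** - **Section 7.2, both documents:** define a safety set of all consented subjects with at least one dose of FTC/TDF, whatever their eligibility. State how exposure and events before consent are handled for subjects already on PrEP. Limit the eligibility restriction to the other summaries.
- **Sections 7.2 and 7.5:** use one criterion term and say whether it covers both inclusion and exclusion criteria.
- **Section 7.5:** keep the eCRF open for anyone treated. Record eligibility and any reason for exclusion for every consented subject, and name this as the source of the exclusion table. This also brings 7.5 into line with Table 1.
- **Sections 3.2 and 5.3:** reconcile the statements on contraindicated subjects, so that their eligibility status is clear.

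The cost is wording in a few sections, a short form for a few subjects and one additional analysis set.

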7.3 Descriptive statistics

Categorical variables will be described by means of absolute and relative frequencies, while continuous variables by means of mean, standard deviation, quartiles, min and max. Analyses will consider data collected at variable observational points, according to clinical practice and clinical judgement. In order to summarize data by time point the nearest available evaluation measurement will be considered (acceptable range).

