2 OBJECTIVES

This study is designed to evaluate implementation of PrEP treatment as a part of the general HIV preventive program in Norway. The target groups are mainly MSM and transgender persons at high risk of HIV infection, as well as other subjects at risk of HIV infection due to their sexual practices.

Objectives include assessment of the following:

- Assess the impact of PrEP on the sexual and psychological health of PrEP users
- Incidence of sexually transmitted infections (STIs) in PrEP users compared to those not taking PrEP
- Assessment of drug compliance
- Incidence of HIV seroconversion despite PrEP
- Frequency and development of drug resistance in subjects who HIV-seroconvert (if any)

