3 POPULATION

3.1 Inclusion Criteria

In order to participate in the PrEP arm of this study the subjects must meet all of the following inclusion criteria:

1. Male, female or transgender persons aged ≥ 18 years who are offered or have started PrEP in routine clinical practice, and 2, 3, 4, 5, 6 or 7 (below).
2. Men who have sex with men (MSM) and transgender persons;
 - a. who have had unprotected anal sex with two or more partners during the last six months and/or
 - b. who have had bacterial sexually transmittable infection(s) during the last twelve months and/or
 - c. who have used post-exposure prophylaxis(PEP) during the last twelve months and/or
 - d. who use recreational drugs when having sex
3. Indication for PrEP is present according to the assessment of the health care provider
4. Men and women who are at high risk of HIV according to their sexual practices
5. HIV-negative partner of a HIV-positive person not yet virologically suppressed by antiretroviral therapy (ART)
6. Sex workers with inconsistent condom use
7. Persons with inconsistent condom use with sexual partners in / from countries with a high prevalence of HIV (COHP)

Subjects who are included in the PrEP arm will act as their own controls regarding possible changes in psychological and sexual health. At the screening visit they will complete questionnaire requesting information related to last 6 months prior to study start. Individuals who seroconvert during the observational period will be transferred to the out-patient clinic for Infectious Diseases as is already standard of care.

Patients diagnosed with HIV in general clinical practice and referred to the out-patient clinic at the Dept. of Infectious Diseases, OUS, will be asked to act as controls to assess their past psychological and sexual health. They will be asked to sign the consent form and answer the same questionnaire as those in the PrEP arm but not followed further in this study.

Frequency of STI reported to the National Institute of Public Health (MSIS) will be compared with the frequency of STIs in the study cohort.

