7 STATISTICAL METHODOLOGY AND DATA MANAGEMENT

7.1 Statistical Analysis Plan

All analyses will be performed by the Sponsor after the study is completed and the database is locked. Statistical programming and analyses will be performed using SAS and/or other validated statistical programs. A detailed statistical analysis plan (SAP) will be described in a separated document.

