7.4 Missing data

Subjects missing data values will not be excluded from the analysis, but their data will not be replaced; frequency of missing data will be given for all analysed variables.

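### As supplied, the methods specify no person-time rate, within-person change or interval for the incidence and own-control objectives, and two stated rules would mislead if applied as written

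*Protocol*

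**What the plan says.** Section 2 of the protocol lists "Incidence of HIV seroconversion despite PrEP" and "Incidence of sexually transmitted infections (STIs) in PrEP users compared to those not taking PrEP" among its objectives. Section 3.1 adds "Subjects who are included in the PrEP arm will act as their own controls regarding possible changes in psychological and sexual health", with the baseline obtained as follows: "At the screening visit they will complete questionnaire requesting information related to last 6 months prior to study start". Section 3.3 likewise takes the own-control reference from the time before inclusion, and it plans to compare STI frequency in the cohort with national surveillance (MSIS).

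The methods offered for this are in section 7. Section 7.3 states "Categorical variables will be described by means of absolute and relative frequencies", gives mean, SD, quartiles, minimum and maximum for continuous variables, and assigns data to time points by the nearest available measurement. Section 7.2 restricts the population: "Data will be described on enrolled subjects undergoing PrEP treatment". Under section 7.4, subjects with missing values stay in, but "their data will not be replaced; frequency of missing data will be given for all analysed variables". Section 7.1 defers the rest: "A detailed statistical analysis plan (SAP) will be described in a separated document".

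The file labelled SAP does not close the gap. It has the protocol's outline and section numbering, repeats 7.1 to 7.4, and promises a separate SAP in its own 7.1. It is another version of the protocol rather than the detailed plan.

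Four other statements matter. Follow-up lasts up to 24 months (5.4). Subjects already taking PrEP may enter, with historical medical information collected back to their PrEP start (4.1). A subject found HIV positive while using PrEP is recorded as a failure of PrEP (3.5). The window for ruling out infection is 12 weeks (4.1), and tests at weeks 2, 4 and 8 are meant to find people already seroconverting at inclusion (4.2).

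**The concern.** The objectives ask how often infections occur over time and how much individuals change. The stated summaries answer neither directly, and none comes with a measure of precision.

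A percentage depends on how long people were observed, so cohorts with the same underlying rate can show different percentages. If an STI percentage means ever positive, repeat infections also disappear from it. If no seroconversions occur, a bare zero does not say what rate has been excluded. Separate means and SDs at each visit do not give the precision of a within-person change.

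Two rules go further than missing detail, because applying them as written would give a misleading result. One takes the time before inclusion as baseline for everyone, although some subjects are already on PrEP by then. The other counts every subject found positive on PrEP as a failure, although the protocol itself expects that some infections may predate the first tablet. At stake are the HIV incidence on PrEP and the own-control result, which carries the study's main aim in section 1.1.

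**Working it through.** The plan has no figure to reproduce: the outline gives sample size as not applicable, and neither file states a dropout rate, SD or correlation. The check is therefore textual, with two illustrations.

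**Objectives against methods**

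- HIV incidence: 7.3 offers a count and a percentage. No person-time denominator or interval is named. No analysis rule separates infections present at PrEP start, and 7.2 does not say how time after stopping is treated.
- STI incidence: 7.3 offers a count and a percentage. No rule distinguishes a new episode from a persistent one.
- Own-control change: 7.3 offers summaries by visit. No change variable or interval is named, though none is ruled out.
- The bracketed acceptable range in 7.3 is an undefined visit window, not a confidence interval.

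**Baseline for existing users.** The Visit 0 questionnaire covers the six months before study start. For someone who has taken PrEP throughout those months, it describes behaviour on PrEP. The historical data in 4.1 are medical information, and no pre-PrEP questionnaire is described for these subjects. Suppose a share p of the cohort are existing users who show no further change, and new starters change by D. The pooled mean change is then (1 − p) × D. The documents do not give p, so the distortion cannot be sized.

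**HIV numerator.** Section 3.5 has one category, while 4.1 and 4.2 recognise two situations: infection present at start and infection acquired on PrEP. The data to separate them are largely collected (early tests and, for recent exposure, a provirus test), but no analysis rule uses them.

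**Illustration 1: one percentage, different rates.** Assume 3 cases in 500 subjects. The percentage is 3/500 = 0.6% whatever the follow-up. The exact Poisson 95% limits for a count of 3 are χ²(0.025; 6)/2 = 0.619 and χ²(0.975; 8)/2 = 8.767.

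| Assumed mean follow-up | Person-years (PY) | Rate per 100 PY (95% CI) |
|---|---|---|
| 2 years | 1000 | 0.30 (0.06 to 0.88) |
| 1.5 years | 750 | 0.40 (0.08 to 1.17) |
| 1 year | 500 | 0.60 (0.12 to 1.75) |

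**Illustration 2: zero events.** The Introduction cites an incidence of 3 per 100 persons per year and 86% protection. If both applied here, the expected rate on PrEP would be 3 × (1 − 0.86) = 0.42 per 100 PY. With no events, the two-sided 95% exact upper limit for the count is χ²(0.975; 2)/2 = 3.689. It falls below 0.42 per 100 PY only above 3.689/0.0042 ≈ 878 PY.

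| Assumed PY | Upper limit per 100 PY with zero events |
|---|---|
| 200 | 1.84 |
| 500 | 0.74 |
| 1000 | 0.37 |
| 2000 | 0.18 |

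At 500 PY and a true rate of 0.42, the expected count is 500 × 0.0042 = 2.1, and zero cases would occur with probability exp(−2.1) = 0.12.

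**The case against.** The strongest reply is that this is a non-randomised, descriptive evaluation with no sample-size claim, that 7.3 is headed as descriptive, and that the detail was deliberately left to another document. Part of this stands: the missing SAP may already contain the rates and intervals, so the finding concerns the text as supplied. The descriptive label does not answer it, however. A rate or a paired change with an interval is still descriptive, and no test or power calculation is being asked for.

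Four stronger readings are tempting and go too far.

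- A reader might infer that the plan cannot estimate incidence at all. New starters have an end-of-study visit planned at 24 months, and for them a percentage over that period is a crude cumulative incidence. The fair statement is that the rate and its precision are not specified.
- A reader might infer that diagnoses at extra visits are ignored. Section 4.2 collects STI data at relevant extra visits, and 7.3 says data from variable observation points are considered. What remains missing is the rule for a new episode.
- A reader might infer that six-month recall at three-monthly visits makes the first follow-up overlap the pre-PrEP period. The questionnaires in Appendix 12.2 are not visible, and Table 1 lists a separate follow-up instrument, which may state its own recall period. This is a query, not a finding.
- A reader might infer that early infections go undetected. The week 2, 4 and 8 tests exist to find them, and HIV-positive subjects are excluded by 3.2. The gap is in how such cases are counted once found.

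Reporting missing-data frequencies under 7.4 makes a changing set of contributors visible, but it does not correct for it.

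**Conclusion.** The point holds for the supplied text and should be fixed before database lock. Neither file specifies a person-time rate, a within-person change or an interval for objectives that need them. The own-control baseline and the single failure category would each mislead if applied as written. The conclusion is conditional: if the separate SAP covers these matters, citing it is enough.

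The size cannot be fixed from the documents. Under the assumed 3 cases in 500 subjects, the same 0.6% stands for rates that differ twofold, and that factor comes entirely from assuming mean follow-up of 1 rather than 2 years. The threshold of about 878 person-years uses the documents' own 3 per 100 and 86%, and it holds only if both apply to this cohort. The effects of existing users and of infections present at PrEP start are unquantified, because the documents give neither share.

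**What to change.** Add the following to 7.3 or to the separate SAP before database lock, or cite that SAP if it already does so. Keep the descriptive tables.

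- **HIV.** Report seroconversions per person-year on PrEP with an exact Poisson 95% CI, giving the upper limit if there are no events. Count time from the later of PrEP start and enrolment, because time before enrolment is free of events by selection (3.2). End at the last HIV test on PrEP or at the first positive test. List separately the infections judged present at PrEP start, using the early tests and any provirus result, and the cases found after stopping.
- **STIs.** Report new diagnoses by organism per person-year from enrolment to the last STI test, including extra visits. Show Visit 0 infections as baseline prevalence, state a new-episode rule, and use a CI that allows for repeat episodes within subject.
- **Own-control change.** Report within-subject change from Visit 0 with a 95% CI from a repeated-measures model, separately for new starters and for subjects already on PrEP at entry. State that dropout related to unobserved behaviour may still bias it, and that a before-after change without randomisation (5.5) is not by itself an effect of PrEP.
- **MSIS.** Show the surveillance figure beside the cohort rate as descriptive context only. The Introduction says the number of sexually active MSM is unknown, and three-monthly screening differs from routine notification.
- **Query.** Check the recall period in the follow-up questionnaire.

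The cost is SAP text and some extra programming on tests and questionnaires already in Table 1, with no added subjects or visits. The main burden is on-PrEP time. Section 6 lists no PrEP stop date, so this time must be built from the prescription and diary records described in 5.2. Data after stopping may be sparse.
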